#### 9.2 Screening and Eligibility assessment

Potentially eligible children whose parents/legal guardians are interested in the study will be visited at their home. Given the importance of maternal immunisation status to inclusion in the study, (i.e. whether an aP vaccine was received during the pregnancy) formal confirmation of receipt of the vaccine will be sought before the first study visit. In order to minimise any delay in infant immunisation, the team defined two strategies to gain confirmation of the maternal immunisation status.

In order to confirm maternal immunisation status one of two approaches will be used.

Either:

1) The mothers will be given access to an online form to take to the GP surgery in order to document their pertussis immunisation status, which will then be provided to the study site.

2) Alternatively, after discussion of the study details, the mothers will be sent a consent form (paper or electronic) giving permission for the study team to access their medical records to obtain this information (this includes consent to access their vaccination history either using their electronic patient record (EPR) or through their GP); Mothers should then return a copy of the signed consent form (paper or electronic). A countersigned form will be provided at the initial study visit.

This consent form is only for collection of the information regarding their immunisation status and not the final study consent for the infant enrolment, and a separate consent is going to be taken for inclusion of the infant in the trial.

The first visit will be delayed until the mother's immunisation status has been confirmed. If the mother's immunisation status cannot be confirmed in the recommended time for the participants to be immunised (between 8 and 10 weeks of age as per inclusion criteria) the participant will be excluded from the study.

In order to assess eligibility of the infant for the study, a qualified doctor will perform the first visit that would include a complete medical history (including review of the red book) and a complete physical examination.

The participants GP and the child health department will be notified of all immunisations administered in the study.

#### 9.3 Informed Consent

Written and verbal versions of the Participant Information and Informed Consent will be presented to the infants parents or legal guardians detailing no less than: the exact nature of the study; what it will involve for the participant; the implications and constraints of the protocol; the known side effects and any risks involved in taking part. The participants parent/legal guardian will be allowed as much time as wished to consider the information, and the opportunity to question the investigator, their GP or other independent parties to decide whether they will participate in the study. Written informed consent will then be obtained. It will clearly state that the parent/guardian is free to withdraw their infant from the study at any time for any reason without prejudice to future care, and with no obligation to disclose the reason. All study staff who will take consent are

appropriately trained and experienced in obtaining informed consent for clinical trials and will be delegated to do so by the CI.

A written informed consent form for the infant must be completed by the parent/legal guardian before any study procedures are performed. A copy of the signed informed consent will be given to the participants parent/guardian and the original will be retained at the study site. GPs will be informed in writing of the participation of the infant registered at their surgery who joins the study.

Maternal consent will be taken for access to medical records where required and as described in section 9.2, above.

#### 9.4. Randomisation, blinding and code-breaking

In this, open label, study there will be no blinding of study staff or families, so no system for unblinding or code-breaking is required. Laboratory staff will have no knowledge of the group assignment of the individual.

Prior to V1, the participants will be randomised to either aP or wP on a 1:1 basis using a electronic randomisation system. The randomisation lists will be generated by the study statistician using block randomisation with a random block size 2 or 4. In case a participant cannot be enrolled for the study after randomisation, the current allocation will not be reused and the randomisation list will be followed until all participants are recruited.

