#### b) Exclusion Criteria

#### Mothers

- Any condition which in the opinion of the investigator may interfere with the ability to fulfil study requirements (this may include plans to move house and language comprehension)
- Receipt of immunosuppressive treatment during pregnancy or known HIV positive.

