#### **9.5 Infant study** (summary of procedures in table 1)

#### 9.5.1 Visit 1: 8-10 weeks of age

- 1. Provide explanation of study
- 2. Obtain written informed consent from parent(s)/ legal guardian(s)
- 3. Perform thorough check of inclusion and exclusion criteria and record findings, including

medical and vaccination history, of relevance to the inclusion/ exclusion criteria

- 4. Details and indications for any prescription medications for infant
- 5. Confirm maternal history of pertussis vaccination in pregnancy

6. Physical examination by study doctor or through the well-baby clinic, in line with the well-baby check and will include examination of the cardiovascular, respiratory, abdominal and neurological systems.

7. Record date of birth and gender for subsequent data analysis

8. Measure and record the participant's temperature.

9. If participant meets all inclusion and exclusion criteria, enrol in study.

10. Open allocation envelope that corresponds to participant number

11. Apply topical analgesia (cream or spray) according to SOP instructions (if parents allow, this could be applied at the beginning of the visit to avoid delays when doing the blood test)

12. Blood sampling: Up to 4mls (0.8-0.9 mls/kg)

13. Collect Mucosal Lining Fluid (MLF) using synthetic absorptive matrices (SAM)

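### Blocks of 2 or 4, printed in an open-label protocol, let staff who track allocations guess many of them, so concealment can be undermined

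*Protocol*

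**What the plan says.** Section 9.4 sets the scheme: "The randomisation lists will be generated by the study statistician using block randomisation with a random block size 2 or 4". Allocation is 1:1, and no stratification factor is named. The same section says that "there will be no blinding of study staff or families", but also that "Laboratory staff will have no knowledge of the group assignment of the individual". An infant who is randomised but cannot be enrolled uses up a place on the list: "the current allocation will not be reused and the randomisation list will be followed until all participants are recruited".

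The text on timing is mixed. Section 9.4 has "Prior to V1, the participants will be randomised to either aP or wP on a 1:1 basis using a electronic randomisation system". Section 9.5.1 lists, after consent and the eligibility check, "Open allocation envelope that corresponds to participant number".

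Some exclusions rest on judgement. For mothers, section 8.1.1 names "Any condition which in the opinion of the investigator may interfere with the ability to fulfil study requirements". For infants, participation in other research is left to the investigator.

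**The concern.** For 1:1 allocation, 2 and 4 are the smallest block sizes available. The study team gives the vaccines, and under section 9.5.1 the wP infants have a separate IPV injection and a longer observation period, so each allocation is plain to those present. The running difference between arms never exceeds 2 and returns to zero at the end of every block. Anyone keeping a tally can therefore guess the under-represented arm, without knowing where blocks begin and end.

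At stake is selection at entry. The protocol itself describes wP vaccines as generally more reactogenic (section 9.11), and the same team arranges first visits and judges eligibility. A visit deferred or a borderline exclusion applied because the next arm is suspected would change who enters each arm. The modified intention-to-treat rule in section 14.1 would not undo this: it counts infants who have had two doses, and an infant turned away beforehand is in no analysis set.

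**Working it through.** **The plan's own figure.** The protocol gives no predictability figure. Its one design calculation (section 7.1.2) reproduces. With log10(135/80) = 0.2272, SD 0.324, 45 per arm and two-sided alpha 0.05, a two-sample t-test has power 0.908, against the stated 90.8%. Inflating 90 for 20% withdrawal gives 90/0.8 = 112.5, so 113, against 114 planned.

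**Inputs.** Block sizes 2 and 4, 1:1 allocation and unblinded staff (section 9.4); 114 infants (section 7.1.1). Assumptions: both sizes equally likely, one list, all earlier allocations known. Rule: when the running totals differ, guess the arm that is behind.

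**Block of 2.** Place 1 is a tie. At place 2 the difference is 1 and the guess is always right. Guessable places: 1. Right: 1.

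**Block of 4.**
- Place 1: tie.
- Place 2: difference 1; right with probability 2/3.
- Place 3: difference 2 with probability 1/3, then always right; otherwise a tie.
- Place 4: difference 1; always right.
- Guessable places: 1 + 1/3 + 1 = 7/3. Right: 2/3 + 1/3 + 1 = 2.

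**Combined, per six allocations (one block of each size).**
- Guessable share: (1 + 7/3)/6 = 55.6%, or about 63 of 114.
- Accuracy when guessing: (1 + 2)/(10/3) = 90.0%, or about 57 right.
- Overall, with ties at 50%: (3 + 0.5 × (6 − 10/3))/6 = 72.2%, or about 82 of 114, against 57 by chance.
- By size of difference: difference 1 on 3/6 = 50.0% of allocations, right (1 + 2/3 + 1)/3 = 88.9% of the time; difference 2 on (1/3)/6 = 5.6%, always right.
- Known for certain: a difference of 2 can arise only midway through a block of 4, so that place and the next are both fixed: (1/3 + 1/3)/6 = 11.1%.

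Simulated lists of 114 agree (55.5% guessable, 89.9% accurate), as does a Bayesian filter that is not told the block boundaries (55.5%, 89.9%, 11.0% certain).

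**Unstated mix of sizes.**

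| Share of blocks that are size 4 | Guessable | Accuracy | Right overall |
|---|---|---|---|
| 0% | 50.0% | 100% | 75.0% |
| 25% | 53.3% | 93.8% | 73.3% |
| 50% | 55.6% | 90.0% | 72.2% |
| 75% | 57.1% | 87.5% | 71.4% |
| 100% | 58.3% | 85.7% | 70.8% |

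**Incomplete knowledge.** If the latest allocation is not yet known, the same rule gives (0.5 + 2/3 + 1/3 + 0.5)/(10/3) = 60% accuracy. With two unknown it is 55%; with three, 50%.

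**Larger blocks (4, 6 and 8 equally likely), same rule, by simulation.**

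| Difference | Share of allocations | Accuracy |
|---|---|---|
| 0 | 36.3% | 50% |
| 1 | 47.8% | 75.4% |
| 2 | 13.6% | 85.2% |
| 3 | 2.2% | 92.5% |
| 4 | 0.2% | 100% |

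Overall 68% are right (about 77 of 114). Allocations predictable with at least 85% accuracy: 13.6 + 2.2 + 0.2 = 16.0%. Under blocks of 2 and 4 the figure is 50.0 + 5.6 = 55.6%.

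**The case against.** A reader might infer that concealment cannot hold, or that selection took place. The documents support neither. The 90% needs complete, ordered knowledge of a single list before the next infant is taken. Infants are enrolled at separate home visits, section 9.4 speaks of lists in the plural, several infants may be pending at once, and places used up by infants who were not enrolled blur the tally if nobody sees them. Even a perfect tracker is at chance on about 44% of allocations. That stands, and it is why the figure is a ceiling.

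The lever is also limited. The maternal criterion concerns ability to meet study requirements, and most other criteria are factual. Staff cannot select directly on baseline antibody, because blood is drawn after the envelope step. The primary endpoint is an IgG concentration measured by staff blind to group, V1 blood is taken to allow baseline adjustment (section 7.1.2), and the primary model adjusts for pre-specified covariates. Parent-reported reactogenicity is open to reporting bias whatever the block size. All of this lowers the stakes for the primary result. It does not protect the make-up of the arms.

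Finally, larger blocks help only by degree. With 4, 6 and 8 the tally is unequal more often (64% of allocations, guessed with 78% accuracy), and the contrast of 16% with 55% depends on where the threshold is put. That too stands; the gain is in near-certain guesses.

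**Conclusion.** The weakness is real and moderate. It is a choice that the protocol states, not detail left to another document. Under equally likely sizes and full tracking, about 56% of allocations can be guessed with 90% accuracy and 72% are right overall; across all mixes of the two sizes the overall figure stays between 71% and 75%. Concealment can be undermined, chiefly to the cost of balance at entry and the open reactogenicity comparison. No bias is estimated here, and predictability is not evidence of selection. The primary comparison is less exposed, and the plan's power is not in question.

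Sections 9.4 and 9.5.1 should also be reconciled on whether the allocation comes from the electronic system before Visit 1 or from an envelope at the visit, and on who sees it when. An allocation known before consent would weaken concealment at any block size.

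**What to change.** In section 9.4, drop the block size of 2, use larger randomly varying blocks (for example 4, 6 and 8), and hold the sizes in a restricted document known only to the statistician who generates the list. The protocol need say only that blocks vary at random.

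The cost is one sentence and a maximum imbalance of 4 infants instead of 2. At worst the arms are 59 and 55, equivalent to 2 × 59 × 55/114 = 56.9 per arm instead of 57, so the effect on power is negligible.

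The protocol does not say whether enrolment is complete. Version 4.1 is dated December 2023, the planned study period ends in June 2024, and infants are followed from about 2 to 13 months of age, so it probably is. In that case the scheme cannot be changed. The report should then disclose the block sizes as a limitation and give, by arm, the number randomised but not enrolled and the baseline antibody concentrations. Those counts would not show infants put off before randomisation.

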#### **9.5 Infant study** (summary of procedures in table 1)

#### 9.5.1 Visit 1: 8-10 weeks of age

- 1. Provide explanation of study
- 2. Obtain written informed consent from parent(s)/ legal guardian(s)
- 3. Perform thorough check of inclusion and exclusion criteria and record findings, including

medical and vaccination history, of relevance to the inclusion/ exclusion criteria

- 4. Details and indications for any prescription medications for infant
- 5. Confirm maternal history of pertussis vaccination in pregnancy

6. Physical examination by study doctor or through the well-baby clinic, in line with the well-baby check and will include examination of the cardiovascular, respiratory, abdominal and neurological systems.

7. Record date of birth and gender for subsequent data analysis

8. Measure and record the participant's temperature.

9. If participant meets all inclusion and exclusion criteria, enrol in study.

10. Open allocation envelope that corresponds to participant number

11. Apply topical analgesia (cream or spray) according to SOP instructions (if parents allow, this could be applied at the beginning of the visit to avoid delays when doing the blood test)

12. Blood sampling: Up to 4mls (0.8-0.9 mls/kg)

13. Collect Mucosal Lining Fluid (MLF) using synthetic absorptive matrices (SAM)

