### 7.1.2 Sample size calculation

Assumptions based on data from unpublished NL study of aP given at 3, 5 and 12m:

- Since the Netherland's vaccine schedule is 2 priming doses in the first 5 months of newborns + 1 booster at 11 months using aP, we will use the GMC of PT antibody at 12m in the unpublished data as our assumption to power the current study, which has a primary outcome at 1 months post ap-booster (13 months).

The GMC of PT on log10 scale= 1.9 (80 mcg/ml)

- Standard deviation of GMC at 13m on log10 scale = 0.324

- Expected difference in post-boost PT-antibody concentration on  $log_{10}$  scale = 0.23 (135 v 80 mcg/ml) derived as a conservative assumption from two previous studies (see above) (Kitchin and Englund)

- Expected withdrawal proportion 20%

A total of 57 infants will be recruited to each arm. With a total of 90 infants in the final analysis, the study will have a 90.8% power to detect the difference between a GMC of 135 and 80 mcg/ml (0.2 on log10 scale) in the wP and aP cohort at a significance level of 0.05. The sample size calculation was done as two-sided hypothesis test using R "pwr" package and validated using PASS v15.0.6.

Blood collection at V1 (before the 2 months immunisations) will be performed in order to allow an adjustment for baseline antibody levels. In order to mitigate any possible cases of infants with previous contact with pertussis and consequently detectable antibodies, infants with previous history of pertussis disease/whooping cough confimed by a diagnostic laboratory test would be excluded.

Written informed consent will be obtained from the mothers of the potential study participants prior to enrolment of each infant participant in order to have access to their immunisation status records before enrolment.

Prior to the infant's enrolment, informed consent will be obtained from parent(s) or the legal guardian (detailed in section 9 (Study procedures), recruitment (9.1) and informed consent (9.3)), after which eligibility against the inclusion and exclusion criteria documented here in section 8.1.1 will be confirmed.

If they are eligible to continue, the participants will have blood samples collected and will be vaccinated by the study team under the schedule set out in the table below. If the participant is not eligible, they will not be enrolled in the study and the infants will need to be vaccinated through the NIP.

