#### 9.6 Blood sampling

Blood sampling will be carried out in line with SOPs. A local anaesthetic cream will be applied for an appropriate period of time prior to each venepuncture. The maximum blood volumes requested for each sample are in accordance with the NIHR Medicines for Children Research Network[57], that states that "per individual, the trial-related blood loss should not exceed **3%** of the total blood volume during a period of **four weeks** and should **not exceed 1% at any single time**. **The total volume of blood is estimated at 80 to 90 ml/kg body weight**"; **3% is 2.7 ml blood per kg body weight** considering a total estimated volume of 90 ml/kg body weight.

For the calculations, we considered the WHO centile curves for girls and boys on the 5th centile as representative of the smallest participant and the visit schedule one-month period. Based on these estimates a maximum of 4 ml of blood could be safely obtained during blood visits for laboratory analysis in participants up to 6 months of age (V1 (baseline), and V5), and a maximum of 6 mls in participants at 12 and 13 months of age (V7, V8). Blood volumes and assays for each group are shown in **table 3** 

If the initial attempt at venepuncture is unsuccessful, verbal consent will be sought from the parents for a further attempt at that visit. No more than two attempts at venepuncture will be made.

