#### 11.1 Name and description of non-investigational product(s)

A local anaesthetic cream (EMLA®/ AMETOP®) will be applied for an appropriate period of time prior to each venepuncture. Written instructions about how the cream should be applied will be given and explained to the parents/guardians.

EMLA 5%® contains Lidocaine 2.5% w/w (25 mg/g) and Prilocaine 2.5% w/w (25 mg/), with marketing authorisation number PL 39699/0088, first approved 16th May 1996 and renewaled on 5th of July 2002.

AMETOP® contains Tetracaine base 4.0% w/w with marketing authorisation number PL 14038/0001 on 09/10/2006.

EMLA® will be the first anaesthetic cream to be supplied to the parents for this population, that can be replaced by AMETOP® in case of previous or new allergy to EMLA®. In order not to increase the length of the visit, the study team can also apply AMETOP® in case the parents/guardians didn't apply the cream before the beginning of the visit, considering that the time for action for AMETOP ® is less (30 minutes) than EMLA® (60 minutes).

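### Visit 1 reveals the arm before the baseline blood and nasal samples, so whether a baseline is obtained can depend on arm; reordering one step removes this at no cost (minor).

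*Protocol*

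**What the plan says.** Protocol 9.5.1 numbers the Visit 1 procedures. The infant is enrolled at step 9. Step 10 is "10. Open allocation envelope that corresponds to participant number". Topical analgesia is step 11, the baseline blood step 12 and the nasal fluid step 13. A second list then gives the vaccines. The only change of order offered concerns the analgesia: "if parents allow, this could be applied at the beginning of the visit to avoid delays when doing the blood test".

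Section 9.4 states that "there will be no blinding of study staff or families", that laboratory staff do not know the group, and that randomisation takes place before Visit 1 through an electronic system.

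Section 7.1.2 gives the purpose of the sample: "Blood collection at V1 (before the 2 months immunisations) will be performed in order to allow an adjustment for baseline antibody levels". Under section 9.6, if the first venepuncture fails, "verbal consent will be sought from the parents for a further attempt at that visit", with two attempts as the limit.

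**The concern.** In an open-label trial, baseline measurements are best completed before anyone at the visit knows the arm. Here they are not. By step 12 the parents of a wP infant know that three injections follow rather than two (section 7.2), including a vaccine that section 9.11 describes as generally more reactogenic. The parents of an aP infant know that theirs will receive the routine product. If the first venepuncture fails, agreement to another is sought with that knowledge. Parents may also withdraw at that moment without giving a reason (section 9.12).

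What is exposed is whether a baseline sample exists, and perhaps its volume. The baseline is the exposure variable in secondary objective 1, the 2-month time point in secondary objectives 4 and 5, the pre-vaccination nasal sample in objective 8, and the source of the baseline adjustment foreseen in 7.1.2.

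**Working it through.** **1. Does anything before vaccination need the arm?** Steps 11 to 13 (analgesia, blood, nasal fluid) are the same in both arms. The first act that differs by arm is the injection in the second list of 9.5.1. Opening the allocation at step 10 gains nothing over opening it after step 13.

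**2. How long is the arm known before the blood draw?** Section 11.1 gives 30 or 60 minutes for the two anaesthetic creams to act. That is an upper bound: step 11 allows a spray, or cream at the start of the visit, so the gap may be only minutes.

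**3. Is the measured value affected?** No. The sample precedes vaccination and the laboratory does not know the group.

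**4. The plan's own power.** Inputs from 7.1.2: GMC 135 v 80, SD 0.324 on the log10 scale, 90 infants analysed (45 per arm), two-sided 0.05.
- Difference: δ = log10(135/80) = 0.2272.
- Noncentrality: λ = δ / (SD × √(1/n₁ + 1/n₂)) = 0.2272 / (0.324 × √(2/45)) = 3.327.
- Power from the noncentral t with 88 degrees of freedom: 90.8%. This reproduces the stated figure.

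**5. An illustrative loss of baselines.** The protocol gives no rate, so 5% and 15% are assumptions. The calculation also assumes that infants without a baseline are dropped and ignores any gain from adjustment. Counts: 45 × 0.95 = 42.75, taken as 43; 45 × 0.85 = 38.25, taken as 38.

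| Missing aP / wP | Analysed | λ | Power |
|---|---|---|---|
| 0 / 0 | 45 v 45 | 3.327 | 90.8% |
| 5% / 5% | 43 v 43 | 3.252 | 89.5% |
| 5% / 15% | 43 v 38 | 3.150 | 87.5% |

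The same 81 infants split 41 v 40 give λ = 3.156 and 87.6%. The cost therefore comes from the number of infants lost; the imbalance itself costs almost nothing.

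**6. Is there bias?** A simulation (4,000 repeats, 45 per arm, true difference 0.227) analysed complete cases with baseline adjustment. All of its settings are assumptions: a baseline–outcome correlation of −0.3, with 5% of aP and an average of 25% of wP baselines missing.
- Missingness depending on arm only: mean estimate 0.227.
- Missingness depending on arm and, within wP, on the baseline value: 0.228.
- Missingness depending on arm and, within wP, on an unmeasured predictor of outcome: 0.211. The bias is 0.211 − 0.227 = −0.016, about 7% of the effect.

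Only the third case is biased.

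**The case against.** The strongest reply is that little follows for the primary result. Section 14.1 defines the modified intention-to-treat set by receipt of two doses and does not require a baseline sample. It plans a mixed model with multiple imputation and pattern-mixture sensitivity analyses, and nothing in it drops an infant who has a 13-month result but no baseline. It refers only to pre-specified covariates, so the link between baseline PT and the primary model rests on 7.1.2. How missing baselines are handled may be settled in the statistical analysis plan, which is not at hand. Even in the 43 v 38 scenario, an assumed baseline–outcome correlation of 0.3 or 0.4, with SD multiplied by √(1 − r²), brings power back to about 90% or 92%. This part of the reply stands, and it keeps the point minor.

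It can also be said that parents have just consented after a full explanation, and that no section suggests wP parents would refuse a second attempt more often. That is true. The point is what the step order permits; the protocol does not show that it happens.

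Third, an infant withdrawn on learning the arm receives no dose and has no 13-month value under either order. Reordering would not keep that infant in the analysis. It would leave a baseline value, which section 9.12 allows to be used, to describe the infant.

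A reader might infer that the baseline PT values are themselves compromised, or that the adjusted comparison is biased. The documents support neither. The values are protected as shown in step 3 of the working, and bias would need an unmeasured link between missingness and outcome for which the protocol gives no basis.

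**Conclusion.** The step order is as described, and it leaves the existence of a baseline sample open to influence by knowledge of the arm for no operational gain. The likely consequence is some loss of precision, mainly for secondary objective 1, which cannot use an infant without a baseline unless the value is imputed, and for the adjustment foreseen in 7.1.2. Infants withdrawn at the reveal would also go undescribed.

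Under the assumed rates and complete-case handling, the loss is about 3 points of power against the stated 90.8%, and about 2 points against equal 5% missingness. Neither the rates nor that handling comes from the protocol. The sample size and the planned power are unaffected. This is a free improvement of minor severity.

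**What to change.** 1. In 9.5.1, move step 10 to after step 13, so that consent, eligibility, enrolment, analgesia, blood and nasal fluid all precede the reveal and vaccination follows it.
2. In 9.4, state that the allocation is revealed to staff and family only after the baseline samples have been taken or attempted.
3. Reconcile 9.4 (electronic randomisation before Visit 1) with the envelope in 9.5.1, and say who can see the allocation before the reveal. Without this, moving step 10 may not conceal the arm from staff.
4. For infants already seen under the current order, report missing baseline samples, and withdrawals between the reveal and the first dose, by arm.

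The cost is one reordered step and a short addition to 9.4, with no extra visit, sample or change in sample size. One practical check is that vaccines for both arms are taken to the visit. Opening an envelope there implies this, but the protocol does not say so.

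Version 4.1 is dated December 2023 and the planned study period ends in June 2024, while Visits 1 and 7 are about 11 months apart (2 and 13 months of age). If recruitment has closed, item 4 is the part that can still be acted on.
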